5 STUDY DESIGN

5.1 Overall Design

This is a pragmatic, single center, feasibility pilot of a cluster randomized quality improvement trial with embedded individual randomization to evaluate implementation strategies to increase the use of evidence-based practices (EBPs) to reduce bleeding in patients who are using combination antithrombotic therapy and who are managed by the Michigan Medicine anticoagulation monitoring service. Two clinician-level strategies will be evaluated: (1) a clinician notification that identifies the patient as high-risk for upper GI bleeding and suggests discontinuing the antiplatelet agent or initiating a PPI; and (2) a clinician notification + nurse facilitation strategy in which a nurse undertakes multiple steps in an effort to overcome barriers to medication optimization. In addition, two patient-level strategies will be evaluated: (1) a patient activation tool; and (2) usual care. Clinicians will be cluster randomized, such that all the patients cared for by a single clinician will receive the same clinician-level notification.

Simultaneously, patients will be individually randomized to one of the two patient-level strategies.

Since this is a pilot study to assess feasibility of delivering all QI implementation strategies and acceptability of the strategies, the study design may be modified during the study period if problems are identified. Any study design modifications will be submitted to the IRB at Michigan Medicine as study amendments and documented in the amendment section on page 6 of this document.

5.2 Scientific Rationale for Study Design

The current study is a pilot quality improvement trial that will inform the design of a larger quality improvement trial with a similar design that will take place in the Michigan Medicine anticoagulation service in the near future. The justification for conducting the pilot study is to ensure that all study components can be feasibly executed. Indeed, it is recommended that pilot studies be undertaken prior to larger scale evaluations.

There are several additional justifications for the study design. Both clinician notification, as well as mailed patient education and activation tools, are commonly used by the anticoagulation service as part of routine clinic practice to improve the safety of patients using warfarin. For example, the anticoagulation clinic previously undertook a quality improvement project that consisted of notifications to clinicians about the potential benefits of discontinuing aspirin in certain patients. The anticoagulation clinic has also produced and distributed materials for patients on self-management of nosebleeds. However, even though these clinician- and patient-facing strategies are considered standard practices, it remains important for the clinic to understand whether such strategies are effective, and whether they justify the significant resource investment of the anticoagulation clinic staff. The study design will help to answer that question in the context of medication optimization to reduce upper GI bleeding.

The study design selected, which can be classified as a factorial study design, is well suited to the objectives of this quality improvement trial because it will allow the simultaneous investigation of two important questions: (1) How a relatively simple notification message to clinicians (“clinician notification”) compares to a simple notification paired with additional steps by the anticoagulation nurse to facilitate medication optimization (“clinician notification with nurse facilitation”). Prior studies have shown that clinician alerts often have weak and inconsistent effects, justifying a more comprehensive clinician-level quality improvement strategy. However, the more comprehensive QI strategy is also more labor intensive for anticoagulation clinic staff, and so it is therefore important to know how effective it is. (2) How effective is a patient-level education and activation tool? While these tools are often used by the anticoagulation service, it is important to confirm their effectiveness and gain a better understanding of how patients use and perceive such tools.

Patients will be cluster randomized within clinicians for the clinician-level QI strategy because if the same clinician received clinician notification for some of their patients and clinician

notification + nurse facilitation for others, this would likely cause some confusion about what services the clinician could expect to receive from the anticoagulation service for any individual patient. The justification for the individual level randomization for the patient level randomization is that it is the best design to make causal inference about the effect of the patient education and activation tool.

Ultimately, this future large-scale cluster randomized trial will identify which combination of QI implementation strategies is most effective in reducing UGIB risk, and that strategy will be used in the future as a part of usual care by the anticoagulation service.

5.3 Justification for Intervention

Upper GI bleeding is a serious risk to patients who use combination antithrombotic therapy. However, both of the available evidence-based medication optimization strategies to reduce upper GI bleeding risk are underused.

This trial will rigorously evaluate strategies that are used by the anticoagulation service to address safety issues that arise surrounding the safe use of warfarin.

5.4 End-of-Study Definition

5.4.1 Group 1

Patient and anticoagulation clinic staff are considered to have completed the study after week 28.

Clinicians are considered to have completed the study 10 weeks after trial entry of the last of the patients within the clinicians' cluster once they have completed the clinician interview (or decline to do so).

5.4.2 Group 2

Patient and clinician participants are considered to have completed the study after week 12.

6 STUDY POPULATION

6.1 Sample size

6.1.1 Group 1

The target sample size for group 1 in the pilot study is 40-51 patients cared for by 12 target clinicians. See sample size determination (below) for a justification of the size.

6.1.2 Group 2

The target sample size for group 2 is 8-16 patients cared for by 8 target clinicians who specialize in primary care.

6.2 Inclusion Criteria

6.2.1 Group 1

For patients:

- Enrollment with the Michigan Medicine anticoagulation monitoring service
- Currently prescribed warfarin with anticipated use for ≥ 90 days on day 1 of trial enrollment, according to the MiChart documentation.
- Currently prescribed an antiplatelet drug (aspirin, clopidogrel, ticagrelor, or prasugrel) according to the MiChart medication list

For clinicians:

- Practicing cardiologists at Michigan Medicine who in the prior year had a face-to-face or virtual visit with a patient who meets eligibility criteria for this study
- Practicing clinicians in any specialty who are designated as the clinician of record with the anticoagulation clinic for a patient who meets eligibility criteria

For anticoagulation clinic staff:

- Participated in the quality improvement project to deliver implementation strategies

6.2.2 Group 2

For patients:

- Enrollment with the Michigan Medicine anticoagulation monitoring service
- Currently prescribed warfarin with anticipated use for ≥ 90 days on day 1 of trial enrollment, according to the MiChart documentation.
- Currently prescribed an antiplatelet drug (aspirin, clopidogrel, ticagrelor, or prasugrel) according to the MiChart medication list

For clinicians:

- Practicing primary care or family medicine clinicians at Michigan Medicine who in the prior year had a face-to-face or virtual visit with a patient who meets eligibility criteria for this study

6.3 Exclusion Criteria

6.3.1 Group 1

For patients:

- Age less than 18
- Currently prescribed a PPI
- Documented intolerance or allergy to PPI use
- Left ventricular assist device
- Heart transplant

For clinicians:

- Cardiologists specializing in electrophysiology unless they are the clinician of record for a patient followed by the anticoagulation service.

For anticoagulation clinic staff

- None

6.3.2 Group 2

For patients:

- Age less than 18
- Currently prescribed a PPI
- Documented intolerance or allergy to PPI use
- Left ventricular assist device
- Heart transplant

For clinicians:

- None

6.4 Patient and Clinician Selection

6.4.1 Group 1

At random, we will choose 12 Michigan Medicine clinicians who either serve as the cardiologist for (n=6), or the (non-cardiologist) clinician of record (n=6) for patients in the anticoagulation clinic. For each of these clinicians, we will include all of their patients who meet eligibility criteria based on chart review. We anticipate the number of included patients will be 40-51. Eligibility will be determined based on information in the electronic health record. All participants will be screened for eligibility in the week prior to study entry.

6.4.2 Group 2

We will select a convenience sample of 8 Michigan Medicine clinicians who are the clinician of record for patients in the anticoagulation clinic and specialize in primary care from a convenience sample. For each of these clinicians, we will include all of their patients who meet eligibility criteria based on chart review. Eligibility will be determined based on information in the electronic health record. All participants will be screened for eligibility in the week prior to study entry.

6.5 Screen Failures

Patients who are ineligible for the study at the time of screening will not be included.

6.6 Strategies for Recruitment and Retention

6.6.1 Group 1

This trial will be conducted as a pragmatic quality improvement initiative in partnership with the Michigan Medicine anticoagulation clinic service. As knowledge of their participation in this study prior to receipt of the QI implementation strategies could result in unintended reactivity, in which the participant changes their behavior in response to knowing they are being observed, and harm the integrity of the study, patient and clinician participants will not be actively recruited for this study prior to delivery of the implementation strategies and no strategies will be used for participant retention. However, to complete the assessments for the study to evaluate the feasibility and acceptability of the Qi strategies, we will contact patients by phone up to 3 times over the period of 2 weeks to administer a brief 5-10 minute phone assessment to assess the accuracy of the electronic health record and determine whether the patient received the implementation strategies. Patient phone numbers will be obtained from the electronic health record and a voicemail will be left for the patient if they are unable to be reached at any of the 3 contact attempts. The research team will also contact clinician and anticoagulation clinic staff participants at their institutional email address to invite them to participate in a one-time, hour long qualitative assessment to elicit feedback about their experience with the implementation strategies and feasibility of continuing the project. Clinician and staff email addresses will be obtained from Michigan Medicine departmental websites or the University directory.

6.6.2 Group 2

This trial will be conducted as a pragmatic quality improvement initiative in partnership with the Michigan Medicine anticoagulation clinic service. As knowledge of their participation in this study prior to receipt of the QI implementation strategies could result in unintended reactivity, in which the participant changes their behavior in response to knowing they are being observed, and harm the integrity of the study, patient and clinician participants will not be actively recruited for this study prior to delivery of the implementation strategies and no strategies will be used for participant retention. The research team will, however, contact clinician participants at their institutional email address to invite them to participate in a one-time, hour long qualitative assessment to elicit feedback about their experience with the implementation strategies and feasibility of continuing the project. Clinician email addresses will be obtained from Michigan Medicine departmental websites or the University directory.

7 STUDY QUALITY IMPROVEMENT STRATEGIES

7.1 Study Implementation Strategy Administration

7.1.1 Quality Improvement Strategy Descriptions

All of the implementation strategies have been documented into clinical protocols approved by the anticoagulation clinic to address upper GI bleeding risk. All study QI strategies will be delivered by anticoagulation clinic staff as part of routine care.

Two clinician-facing implementation strategies will be evaluated.

1. **Clinician Notification:** An anticoagulation clinic nurse sends a templated message to the patient's target clinician that points out the patient's high risk for upper GI bleeding, summarizes guidelines on appropriate antiplatelet drug use and PPI gastroprotection, and recommends that the clinician consider either discontinuing the patient's antiplatelet drug or initiating a PPI for gastroprotection.
2. **Clinician Notification + Nurse facilitation:** An anticoagulation clinic nurse sends a templated message to the target clinician, similar to the clinician notification strategy. However, the message also includes clinical details about the patient's indication for antiplatelet therapy, ascertained by the nurse during chart review, and is intended to streamline decision-making by the clinician. In addition, the nurse will pend orders for medication changes if given instructions by the clinician and will communicate any recommendations to the patient on the clinician's behalf.

In addition, two patient-facing implementation strategies will be evaluated:

1. **Patient Activation:** A written guide to educate patients about their risk for bleeding and encouraging patients to talk with their clinician about medication changes to reduce their bleeding risk. This will be sent to patients through their preferred mode of communication (mail or patient portal). All patients will only be sent the guide once.
2. **Usual care:** With usual care, the anticoagulation clinic will not send the patient activation guide or other project-specific materials to the patient.

7.1.2 Administration and/or Dosing

N/A

7.2 Fidelity

7.2.1 Anticoagulation Nurse Training

Prior to the start of the study, the participating anticoagulation clinic staff will attend an instructional meeting with a research team member on how and when to administer the QI strategy components and how to document delivery of strategies in the electronic health record. This training is anticipated to be 90 minutes long.

For anticoagulation clinic staff, the implementation strategies and how to perform them are additionally described in anticoagulation clinic protocol documents.

7.2.2 Quality Improvement Strategy Delivery

Anticoagulation clinic nurses will have pre-scripted messages to use as part of clinician-facing implementation strategies.

Nurses will also have an example script available to use when talking with patients about medication changes.

7.2.3 Quality Improvement Strategy Receipt & Enactment

7.2.3.1 Group 1

Chart review will be performed for all patients to ensure that they received the implementation strategies to which they were randomized.

For patients randomized to the activation brochure, they will be questioned about receipt of the brochure, their understanding of the brochure and its purpose during patient assessment #2 at week 5-8.

7.3 Measures to Minimize Bias: Randomization and Blinding

Assignment to one of two clinician-level QI strategies will be done at the cluster level according to the identity of the clinician to be contacted. The cluster of patients cared for by each anticoagulation clinic target clinician will be randomized 1:1 to get either clinician notification (CN) or clinician notification + nurse facilitation (CN+NF). Patients will also be individually randomized to receive the patient activation guide or to a usual care arm.

Neither patients nor clinicians can practically be blinded.

As this is a pragmatic, quality improvement trial, there is no intention to blind anticoagulation clinic staff or research team members to group assignment.

7.4 Concomitant Therapy

Patients in this study will continue to receive all other usual care through the anticoagulation clinic. They will not be prevented from seeking or being exposed to any other medications or information from other sources during the study period or from seeking care from other clinicians.

7.5 Rescue Therapy

N/A

8 END-OF-INTERVENTION/END-OF-STUDY

8.1 Discontinuation of Intervention

8.1.1 Group 1

Use of the implementation strategies will be discontinued for patients who discontinue warfarin therapy or are closed to the anticoagulation clinic service during the first 5 weeks of study participation. Such patients will not be included in the analyses, and will not receive patient assessment #1, #2, or #3.

For patients who discontinue warfarin or are closed to the anticoagulation clinic between week 5 and the end of the study, they will be contacted for patient assessment #1 and #2 but not #3. They will be included in the analysis of the primary and secondary outcomes, as well as the

exploratory outcomes, except those related to patient assessment #3 (e.g., medication adherence, appropriateness of antiplatelet therapy at week 15-17).

8.1.2 Group 2

Use of the implementation strategies will be discontinued for patients who discontinue warfarin therapy or are closed to the anticoagulation clinic service during the first 3-5 weeks of study participation. Such patients will not be included in any analyses.

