The study is designed as a pilot cluster randomized quality improvement trial. For each patient, a target clinician will be identified, defined as either a cardiologist at Michigan Medicine, if the patient has seen one in the past year, or else the clinician of record on file with the anticoagulation service. For each patient, assignment to one of two clinician-level QI strategies will be done at the cluster level according to the identity of the target clinician. Each clinician (cluster) will be randomized 1:1 to receive either clinician notification (consisting of a notification message sent in the electronic health record) or clinician notification + nurse facilitation (consisting of a similar notification, but which additionally includes provision of clinically relevant information identified on chart review, along with other steps to facilitate appropriate care). Separately, patients will be individually randomized to receive an activation guide that provides patient education and encouragement to discuss medication optimization with their clinicians, or to usual care. Following delivery of the QI strategies, patients, clinicians, and anticoagulation staff will be invited to participate in semi-structured interviews about their experiences with and perceptions of the QI strategies.

Group 1: Primary Objective: To explore the feasibility of patient participation in a one-time assessment of medication use following delivery of the QI strategies.

Group 1: Secondary Objectives: To explore the feasibility of delivering QI strategy components to clinicians and patients as intended.

Group 2: Primary Exploratory Objective: To explore the feasibility and appropriateness of the QI strategies from the perspective of primary care clinicians to inform a future clinic-wide trial.

Endpoints*:

Group 1: Primary Endpoint: The proportion of randomized patients who complete a brief phone assessment (patient assessment #1) at week 5.

Group 1: Secondary Endpoints: The proportion of patients and clinicians who received the QI strategies to which they were randomized.

Group 1: Exploratory Endpoints: Multiple additional quantitative endpoints will be evaluated, as documented in the section 4 of the protocol.

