4 OBJECTIVES AND ENDPOINTS

4.1 Objectives and Endpoints (Group 1)

OBJECTIVES	ENDPOINTS
Primary	
To explore the feasibility of patient participation in a one-time assessment of medication use following delivery of the QI strategies.	Proportion of patient participants who are able to be contacted by phone and are willing to participate in and fully complete patient assessment #1, related mainly to medication use (week 5 interview).
Secondary	
To explore the feasibility of delivering QI strategy components as intended.	Proportion of participants who received all implementation components to which they were randomized in the appropriate time frame.
Exploratory	
To explore additional aspects of the feasibility of recruitment.	Proportion of randomized patients able to be reached by phone after three attempts for patient assessment #1 at week 5. Average number of phone call attempts to reach each patient for patient assessment #1 at week 5. The number of anticoagulation clinic patients who meet eligibility criteria for the AEGIS trial on the first day of the pilot study according to the EHR workbench report.
To explore changes in the proportion of eligible patients during the study duration.	The proportion of all patients in the anticoagulation clinic who meet eligibility criteria for the study, regardless of whether they are included, who discontinued warfarin or were otherwise closed to the anticoagulation service during the study period. The proportion of patients who were randomized who discontinued warfarin or were closed to the anticoagulation clinic service during the participants' study duration.

OBJECTIVES	ENDPOINTS
To explore the accuracy of the electronic health record's medication list for ascertaining inclusion criteria	
The proportion of randomized patients who, retrospectively, report that they had been using antiplatelet therapy at baseline during patient assessment #1 at week 5.
 
The proportion of randomized patients who, retrospectively, report that they had been using PPI at baseline during patient assessment #1 at week 5.
 
The proportion of randomized patients who met inclusion criteria based on retrospective medication use in patient assessment #1 at week 5.

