9.5 Assessment of the Secondary Endpoint

9.5.1 Group 1

The proportion of patients who received all implementation strategies to which they were assigned will be determined by EHR chart review in the 6 months following the trial.

9.5.2 Group 2

N/A

9.6 All Other Study Assessments – Group 1

Assessment of all exploratory study endpoints will be performed by a research assistant using chart review or semi-structured interview assessments conducted by phone or zoom call with patients,

clinicians, and anticoagulation clinic staff. There will be no assessments that require physical exams, radiology, biological specimens or laboratory evaluations.

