11.2 General Statistical Approach

11.2.1 Group 1

For the primary and secondary analyses, all participants who undergo randomization will be analyzed. Proportions with confidence intervals will be calculated.

11.2.2 Group 2

For the primary and secondary exploratory analyses, all participants who undergo randomization will be analyzed. Proportions with confidence intervals will be calculated.

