11.5 Analysis of the Primary Endpoint(s)

11.5.1 Group 1

We will calculate the proportion of randomized patients that complete the patient assessment at week 5. We will estimate the confidence interval using the normal approximation to the binomial distribution. We will accept this hypothesis if the two-sided confidence interval ($\alpha=0.05$) for the primary endpoint excludes 0.66.

11.5.2 Group 2

Qualitative analysis will be performed to explore clinician perceptions of the intervention strategies for the primary exploratory endpoint.

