11.6 Analysis of the Secondary Endpoint(s)

11.6.1 Group 1

We will calculate the proportion of randomized patients that received all implementation components to which they were randomized in the appropriate time frame. We will estimate the confidence interval using the normal approximation to the binomial distribution. We will accept the hypothesis if the two-sided confidence interval (alpha=0.05) for the secondary endpoint excludes 0.66.

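### Section 8.1.1 drops early leavers from the Group 1 primary and secondary analyses, while section 11 analyses everyone randomized

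*Combined protocol and SAP*

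**What the plan says.** Section 8.1.1 covers Group 1 patients who stop warfarin or are closed to the clinic in the first 5 weeks of participation. Strategy delivery ends for them, and the section continues: "Such patients will not be included in the analyses, and will not receive patient assessment #1, #2, or #3". Its second paragraph deals with patients who leave from week 5 onward: "They will be included in the analysis of the primary and secondary outcomes".

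Other current sections set a different denominator:

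- Synopsis (1.1), primary endpoint: "The proportion of randomized patients who complete a brief phone assessment (patient assessment #1) at week 5".
- 11.2.1: "For the primary and secondary analyses, all participants who undergo randomization will be analyzed".
- 11.5.1, primary analysis: "We will calculate the proportion of randomized patients that complete the patient assessment at week 5".
- 11.6.1, secondary analysis: "We will calculate the proportion of randomized patients that received all implementation components to which they were randomized in the appropriate time frame".

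Under 11.5.1 and 11.6.1, each hypothesis is accepted if the two-sided 95% normal-approximation interval excludes 0.66. Section 4.1 also lists an exploratory endpoint that needs the early leavers: "The proportion of patients who were randomized who discontinued warfarin or were closed to the anticoagulation clinic service".

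**The concern.** For an event the protocol itself foresees, the denominator of the only primary endpoint is defined in two incompatible ways. Two analysts who each follow the document can report different completion rates and, near the threshold, opposite conclusions about feasibility.

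The two rates also answer different questions. One is completion among everyone randomized, which is what the synopsis and section 11 state. The other is completion among patients still on warfarin and enrolled at week 5.

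The secondary endpoint has the same conflict through 11.2.1 and 11.6.1. Its direction cannot be fixed in advance, because some early leavers will already have received every component due to them and others will not. Read literally, 8.1.1 also leaves it unclear whether early leavers count in the 4.1 discontinuation endpoint.

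**Working it through.** **Can the passages be read together?**

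- *Does the exclusion cover only assessment-based exploratory outcomes?* No. The second paragraph of 8.1.1 puts later leavers into the primary and secondary outcomes. That contrast has a point only if the first paragraph takes early leavers out of those outcomes.
- *Are early leavers not yet randomized?* No. The schedule in 1.3 places randomization before week 1. Section 9.1.1 lists entering patients for the nurses with their assigned strategies.
- *Does 8.3.1 settle it?* No. It covers patients who cannot be reached, and early leavers are not called at all.

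**Inputs.** 40 patients and an 80% rate (11.1.1); target range 40 to 51 (6.1.1); threshold 0.66 (11.4.1); 95% normal-approximation interval (11.5.1). The number of early leavers, k, is not given. I assume 0 to 4.

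**The plan's own figure.** Half-width = 1.96 × √(0.80 × 0.20 / 40) = 0.124, consistent with the stated precision of within 13 percentage points.

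**One early leaver.** Lower limit = p − 1.96 × √(p(1 − p)/n), where p = completers/n. The hypothesis is accepted if this exceeds 0.66.

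| Randomized | Completers | All randomized (section 11) | Early leaver removed (8.1.1) |
|---|---|---|---|
| 40 | 31 | 31/40 = 77.5%, lower limit 0.646, not accepted | 31/39 = 79.5%, lower limit 0.668, accepted |
| 51 | 39 | 39/51 = 76.5%, lower limit 0.648, not accepted | 39/50 = 78.0%, lower limit 0.665, accepted |

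With everyone in the denominator, acceptance needs 32/40 (lower limit 0.676) or 40/51 (0.671).

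**Which counts reverse the result, and how likely are they?** For each k, I list the completer counts x that pass with denominator N − k and fail with denominator N. Their probability is the sum of Binomial(N − k, 0.80) over those counts. The 80% is the planning value in 11.1.1, applied here, as an assumption, to patients still enrolled.

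| k | N = 40: counts | Probability | N = 51: counts | Probability |
|---|---|---|---|---|
| 0 | none | 0 | none | 0 |
| 1 | 31 | 0.16 | 39 | 0.13 |
| 2 | 31 | 0.16 | 39 | 0.14 |
| 3 | 30–31 | 0.31 | 38–39 | 0.28 |
| 4 | 29–31 | 0.44 | 37–39 | 0.42 |

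**Other completion rates.** With k = 1, the probability at 70% and 90% completion is 0.064 and 0.023 (N = 40), or 0.060 and 0.006 (N = 51). With N = 40 and 85% completion, it is 0.31 for k = 3 and 0.48 for k = 4.

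**Not conditioning on k.** If each patient leaves early with an assumed probability of 2% and 80% of the rest complete, the chance of disagreement is about 0.10 at either sample size. At 5% it is 0.21 (N = 40) or 0.24 (N = 51).

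**The case against.** The strongest reply has five parts.

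- *The endpoint may be about reachability.* Section 4.1 defines the primary endpoint through ability to be contacted and willingness to take part, and 9.4.1 bases it on up to three contact attempts. Patients whom the protocol bars from being called have no attempts, and counting them as non-completers mixes clinic attrition with phone feasibility. This has some force: either denominator could be defended if the plan adopted one. But neither section restricts the denominator, and 11.2.1 is explicit.
- *The probabilities are near their peak.* An 80% rate puts the expected count close to the decision boundary. This is right for one or two exclusions, where the risk falls sharply at 70% or 90%. It is less so at 85% with three or four exclusions from 40. The 80% is also the plan's own value.
- *Early loss should be small.* Anticipated warfarin use of at least 90 days (6.2.1) and eligibility checks just before entry (6.4.1, 9.1.1) point that way. This stands.
- *Little hangs on the result.* The objective is exploratory, and no passage ties 0.66 to a decision about the larger trial. This limits the consequence. It does not settle which rate is to be reported.
- *The secondary endpoint and 4.1 are weaker ground.* The synopsis does not say randomized patients for the secondary endpoint, so that part rests on 11.2.1 and 11.6.1. The effect there is not quantified and may be small, since first delivery is scheduled early. The 4.1 discontinuation endpoint would make little sense without early leavers, so its intent is fairly clear.

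**Conclusion.** The contradiction is real, sits in current text, and affects the primary and secondary endpoints of Group 1. For the primary endpoint, 8.1.1 can only leave the completion rate unchanged or raise it. A single early leaver can reverse the acceptance decision, at exactly 31 completers of 40 or 39 of 51.

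With 1 to 4 early leavers and 80% completion among the rest, the chance of a reversal is 0.16 to 0.44 (40 randomized) or 0.13 to 0.42 (51 randomized). Those figures rest on an assumed number of leavers, probably towards the low end. With none, the two rules agree. This must be fixed, because the denominator of the primary endpoint has to be settled before the result can be read.

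Group 2 has the same conflict between 8.1.2 and 11.2.2, with descriptive consequences only.

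**What to change.** Amend 8.1.1 so that early discontinuation ends strategy delivery and patient calls, as now written, but does not remove the patient from the analysis. Then:

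- Keep all randomized patients in the primary denominator and count early leavers as not completing assessment #1.
- Score the secondary endpoint for early leavers from the chart review in 9.5.1, which "will be determined by EHR chart review in the 6 months following the trial". State how components not yet due at departure are scored.
- Report completion among patients still enrolled at week 5 as a labelled sensitivity analysis.
- State that the 4.1 discontinuation endpoint includes early leavers.
- Align 8.1.2 with 11.2.2 for Group 2.

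The cost is wording in 8.1.1, 8.1.2 and section 11, plus a line for the 4.1 endpoint, with the IRB approval that 13.2 requires for any amendment. No new data, calls or patients are needed. The primary rate may come out slightly less favourable. If Group 1 outcome data are already in hand when the change is made, the amendment should say so.
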